4.2.2 Restrictions

4.2.2.1 Restrictions regarding concomitant treatment

The medications (or classes of medications) listed in [Table 4.2.2.1:1](#) must not be taken for the specified times prior to randomisation and for the whole duration of the study. If prohibited medication is used during the study for any indication, the patient must discontinue use of the prohibited medication if he/she wants to continue in this study. If a patient receives a live virus during the study, they must be discontinued.

Proprietary confidential information © 2016 Boehringer Ingelheim International GmbH or one or more of its affiliated companies
Table 4.2.2.1:1 Restricted medications

Medication or class of medications	Restriction duration (through EOO Visit)
guselkumab, tildrakizumab	not allowed prior or during trial participation
briakinumab, secukinumab (Cosentyx®), ustekinumab (Stelara®)	6 months prior to randomisation
brodalumab, ixekizumab	4 months prior to randomisation
adalimumab (Humira®), infliximab (Remicade®)	12 weeks prior to randomisation
investigational products for psoriasis (non biologics)	
etanercept (Enbrel®)	6 weeks prior to randomisation
live virus vaccinations	6 weeks prior to randomisation
investigational device or product (excludes psoriasis products)	
other systemic immunomodulating treatments (e.g. methotrexate, cyclosporine A, corticosteroids ¹ , cyclophosphamide, tofacitinib (Xeljanz®), apremilast (Otezla®))	30 days prior to randomisation
other systemic psoriasis treatments (e.g. retinoids, fumarates, any other drug known to possibly benefit psoriasis)	
photochemotherapy (e.g., PUVA)	
phototherapy (e.g., UVA, UVB)	14 days prior to randomisation
topical treatment for psoriasis or any other skin condition (e.g. corticosteroids ² , vitamin D analogues, vitamin A analogues, pimecrolimus, retinoids, salicylvaseline, salicylic acid, lactic acid, tacrolimus, tar, urea, andanthralin, α-hydroxy, fruit acids)	

¹ No restriction on corticosteroids with only a topical effect (e.g. inhalant corticosteroids to treat asthma or corticosteroid drops used in the eye or ear).

² **Exception:** Topical steroids of US class 6 (mild, such as Desonide) or US class 7 (least potent, such as hydrocortisone) will be permitted for use limited to the face, axilla, and/or genitalia with a restriction of use within 24 hours prior to clinic visits when PASI is assessed.

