7.3.3 Further endpoint analyses

Further endpoints will be summarized, with number and proportion of responders for dichotomous endpoints and mean, median, SD and IQR presented for continuous variables.

Time to onset of *Endpoint*, the time to event will be calculated as:

- Time to first onset (with observed event) = [date of first onset] – [date of first active treatment] + 1
- If a patient never attains *Endpoint* (e.g., PASI75 or PASI90), then that patient's time to first onset will be censored at the last visit where the *Endpoint* was measured (e.g., PASI).

Time to Loss of *Endpoint* will only be performed for patients that are re-randomised at Week 28 (i.e., Arms A and B defined in Section 7.2), where day 0 is defined as the date of the Week 16 visit. Time to loss is defined using the following algorithm:

- a) Never attains *Endpoint* (Failure at day 0)
- b) After achieving *Endpoint*, patient will be a failure if they subsequently do not achieve *Endpoint* and either discontinue from the study or switch therapy while still not achieving *Endpoint*. Time to failure will be calculated using date of first failure to achieve *Endpoint*.
- c) Patients that take prohibited meds to treat Psoriasis will be counted as failures at the time when they first take the prohibited med.
- d) Patients that switch therapy while maintaining response will be censored at their last measurement prior to switching treatment. A switch from active medication to Placebo does not constitute a change in treatment.
- e) Patients who maintain *Endpoint* throughout the study will be censored at their last measurement.

Time to Loss of *Endpoint* (from time of achieving *Endpoint* or from specific point in time) will be defined as above but only for those patients that have achieved *Endpoint*.

All Time to Event endpoints will be presented using Kaplan-Meier curves with comparisons made between treatment groups using stratified Log-Rank test. Further information will be provided in the TSAP.

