7.5 HANDLING OF MISSING DATA

Every effort should be made to collect complete data at all visits.

The following rules will be used to impute for missing data:

- For all non-binary endpoints, last observation carried forward (LOCF) will be used to impute missing values
- For all binary endpoints (i.e. endpoints that are either 1 (patient responded) or 0 (patient did not respond)):
 - If no data after that visit*, then impute as failure (NRI [No Response Imputation])
 - If data at visits* before and after, only impute as success if both visits are successes; else impute as failure

* Patients that take prohibited medications to treat Psoriasis will be treated the same as those that discontinued from the trial – i.e. subsequent visits following start of prohibited medication will be considered as failure for binary endpoints.

Missing items from the PRO questionnaires will be handled according to the measure instructions ([Section 10.7](#)). If there is no data for a particular visit, then it will be imputed following the same rules as described above.

Sensitivity analyses to assess the robustness of the hypothesis testing results will include the following methods where applicable:

- LOCF (for binary endpoints)
- Logistic regression

- Mixed effect Model Repeat Measurement (MMRM) (for continuous endpoints)
- Multiple imputation (for binary endpoints)

Of note, for randomized withdrawal analyses, subjects who received retreatment will be counted as non-responders in all visits after the date of retreatment.

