3.0 Introduction

This statistical analysis plan (SAP) describes the statistical analysis to be completed by the AbbVie Clinical Statistics Department for study Protocol 1311.4 dated 28 July 2016.

This SAP will provide details to further elaborate statistical methods as outlined in the Protocol 1311.4 and will describe analysis conventions to guide the statistical programming work. The SAP will be signed off before the study database is locked.

Analyses will be performed using SAS® version 9.4 (SAS Institute, Inc., Cary, NC 27513) or higher using the UNIX operating system.

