10.1.3 Analyses of Time-to-Event Variables

Time to first achievement of endpoints will only be performed in ITT_A1 up to Week 16. The time to event will be calculated as:

- Time to first achievement (with observed event) = [date of first achievement] – [date of first dose] + 1
- If a subject never attains Endpoint at the end of evaluation period, that subject's time to first achievement will be censored at the last visit where the variable was measured

Time to loss-of-response (and time to relapse) endpoints will only be performed in ITT_B_R Population among those who achieved response at Re-Randomization. The time to failure events will be calculated as:

- Subjects will be considered as failures if they subsequently lost the response, or discontinue from the study due to AE of "Worsening of disease under study," or receive retreatment with risankizumab.
- Time to failure events = [date of failure] – [date of first dose in Part B] + 1
- Subjects who maintain Endpoint throughout the study, or discontinued from the study due to reasons other than above, will be censored at their last measurement.

Both time to first achieving endpoints and time to loss-of-response endpoints will be analyzed using Kaplan-Meier estimates for each treatment group. In the ITT_A1 and ITT_B_R populations, treatments will be compared using stratified Log-rank test.

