10.1.4 Missing Data Imputations

Missing data will be imputed using the following methods for the efficacy analyses:

- Non-Responder Imputation (NRI): the NRI analysis will categorize any subject who does not have evaluation during a specific visit window as a non-responder for that visit. The only exception is when the subject is a responder both before and after a specific visit window, then the subject will be categorized as a responder for the visit. Only observations within the same analysis period will be used except for summary of ITT_A2 from ARM 1, where subjects' observation from Part A1 can be used since the treatment is the

same. The NRI will be the primary approach in the analyses of categorical variables.

- Last Observation Carried Forward (LOCF): The LOCF analyses will use the last observed non-missing evaluation (last completed non-missing evaluation, from composite endpoint) from the previous visit within the particular period for efficacy measures assessed to impute missing data at later visits in the same period. Baseline efficacy evaluations will not be carried forward. Of note, post-baseline observations from Part A1 can be carried forward to ITT_A2 subjects from ARM 1 since treatment is the same. LOCF will be the primary approach in the analyses of continuous variables, and the secondary approach in the analysis of categorical variables.
- As-Observed Cases (OC): The as-observed analysis will not impute values for missing evaluations, and thus a subject who does not have an evaluation on a scheduled visit will be excluded from the as-observed analysis for that visit. As-observed analysis will be the secondary approach in the analysis of continuous variables.
- Multiple Imputation (MI): The MI will be used as sensitivity approach to impute missing data in primary and ranked secondary endpoints. The variables to be included in the imputation model are listed below. If MI is not applicable due to the nature of our data (e.g., MCMC algorithm does not converge), logistic regression or mixed effect model repeat measurement (MMRM) methods will be applied as sensitivity approach, whichever applicable.

The Multiple Imputation analysis will be carried out in three steps.

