- Imputation of missing data. The imputation will be generated for each efficacy endpoint measurement. The variables to be included in the imputation model are: Baseline disease severity (PASI and sPGA), Baseline weight (continuous variable), treatment group, actual prior TNF antagonist exposure, and measurements at each visit from randomization (or re-randomization) up to the end of the analysis period. For each endpoint, 20 'complete' datasets will be generated using SAS PROC MI. The imputed post-baseline measurements

will be rounded to the same precision as the observed data before the determination of responder status (e.g., PASI 90).

- Analysis of imputed data sets. A CMH test, stratified by stratification factors, will be used to analyze categorical endpoints in each imputed dataset.
- Synthesis of imputation and analysis results. SAS PROC MIANALYZE will be used to generate the final inferences of the risk difference between treatment groups.

Of note, subjects who discontinued due to AE of "Worsening of disease under study," or received retreatment with risankizumab for relapse during Part B, will be counted as non-responders in all visits thereafter in the NRI and MI analyses, and will have their last observation prior to discontinuation or retreatment with risankizumab carried forward in the LOCF analyses.

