14.0 Summary of Changes

14.1 Summary of Changes Between the Latest Version of Protocol and the Current SAP

- Defined analysis populations (including the Per-protocol population) in detail.
- Clarified independent null hypothesis test hierarchy in the ITT Population in Part B consisting re-randomized subjects.
- Added additional ranked secondary endpoint to the ITT Population in Part B consisting re-randomized subjects: achievement of sPGA of clear or almost clear (0 or 1) at Week 104.
- Pre-specified Areas of Safety Interest.

14.2 Summary of Changes Between the Previous Version and the Current Version of the SAP

Updated Table 25, Table 27, and Table 28 based on Integrated Summary of Safety SAP.

Updated the end day for inclusion concomitant medications, based on Integrated Summary of Safety SAP.

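### The SAP leaves out the protocol rule that prohibited psoriasis medication makes a patient a non-responder, and does not declare the change

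*SAP*

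**What the plan says.** **Protocol.** Section 7.5 treats patients who take prohibited medication for psoriasis like those who discontinued: "subsequent visits following start of prohibited medication will be considered as failure for binary endpoints". Section 7.3.3(c) sets the matching rule for time to loss of response: "Patients that take prohibited meds to treat Psoriasis will be counted as failures at the time when they first take the prohibited med". Section 4.2.2.1 lets such a patient stay in the trial: "the patient must discontinue use of the prohibited medication if he/she wants to continue in this study". Section 3.3.4.1 asks that visits be completed where possible even after study medication stops.

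**SAP.** Under 10.1.4, "the NRI analysis will categorize any subject who does not have evaluation during a specific visit window as a non-responder for that visit", with an exception when the patient responds both before and after the gap. A closing note adds two events that override later data. Subjects who discontinued for an adverse event of worsening disease, or who "received retreatment with risankizumab for relapse during Part B, will be counted as non-responders in all visits thereafter in the NRI and MI analyses", are the only ones named. For time to loss, 10.1.3 says "Subjects will be considered as failures if they subsequently lost the response, or discontinue from the study due to AE of" worsening disease, and adds risankizumab retreatment as the third event.

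The SAP mentions prohibited treatment only as a deviation count in 7.4. Section 14.1, headed "Summary of Changes Between the Latest Version of Protocol and the Current SAP", lists four items: analysis populations, the Part B hypothesis hierarchy, the Week 104 endpoint and Areas of Safety Interest.

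**The concern.** SAP 3.0 says that the document "will describe analysis conventions to guide the statistical programming work", so a programmer will build responder status from 10.1.4. Outside the two named events, NRI and MI alter only missing values. A patient who used another psoriasis therapy, stayed under observation and was then scored PASI 90 or sPGA 0/1 is a responder under the SAP and a failure under the protocol. This applies to the co-primaries, the Part B primary and the ranked secondaries, all of which are binary.

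The bias can go either way. Masked failures in the placebo or withdrawal arm shrink the difference, and help from another therapy in the active arm inflates it. Time to loss of response is affected too, but those are further endpoints outside the testing hierarchy.

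**Working it through.** **1. The texts side by side**

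| Event | Protocol 7.5, binary | SAP 10.1.4, NRI/MI | Protocol 7.3.3, time to loss | SAP 10.1.3, time to loss |
|---|---|---|---|---|
| Retreatment after relapse | failure thereafter | failure thereafter | not named as a failure event | failure |
| Prohibited psoriasis medication | failure thereafter | not named | failure at first use | not named |

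The SAP carries over the retreatment rule from protocol 7.5 but not the prohibited-medication rule in the same section. A version mismatch does not explain this. The SAP cites the protocol of 28 July 2016, and the log of the later amendment lists no change to 7.5 or 7.3.3. The per-protocol criteria in SAP 5.1 do not exclude these patients, although protocol 7.3 names restricted medication as an important violation.

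**2. Who is affected**

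These are patients who used prohibited psoriasis medication, remained under observation, were not retreated for relapse, and have an observed response at the endpoint visit. Patients who leave for rescue have a missing endpoint and are already non-responders under NRI.

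**3. The plan's own Part B figure**

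Inputs from protocol 7.7: response 90% vs 75%, ratio 1:2, two-sided 0.05, power 90%. With pooled variance, the mean rate is (0.90 + 2 × 0.75)/3 = 0.80 and

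n = [1.96 √(0.80 × 0.20 × 1.5) + 1.2816 √(0.09 + 0.1875/2)]² / 0.15² = (0.960 + 0.549)² / 0.0225 ≈ 101.3, rounded up to 102.

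This reproduces 102:204, and 306/0.8 = 382.5 gives 383.

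**4. Power of the planned test**

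Expected numbers: 400 × 0.8 = 320, split 1:2 as 107:213. With one stratum the variance in SAP 10.1.1 reduces to p₁(1−p₁)/n + p₂(1−p₂)/m, and power ≈ Φ(difference/SE − 1.96). With no masking:

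SE = √(0.09/107 + 0.1875/213) = 0.0415; 0.15/0.0415 − 1.96 ≈ 1.65; power 0.951.

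Now take 90% and 75% as the rates under the protocol rule, and let some failures count as responses under the SAP. The fractions are assumptions. The last column is a simulation of the stratified statistic (200,000 runs, assumed stratum shares 50/20/20/10, equal rates across strata).

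| Masked failures | Rates, % | Difference, points | Power, one stratum | Power, stratified |
|---|---|---|---|---|
| none | 90 vs 75 | 15 | 0.951 | 0.942 |
| withdrawal arm, 1 point (about 2 patients) | 90 vs 76 | 14 | 0.925 | 0.915 |
| withdrawal arm, 3 points (about 6) | 90 vs 78 | 12 | 0.841 | 0.833 |
| withdrawal arm, 5 points (about 11) | 90 vs 80 | 10 | 0.707 | 0.709 |
| 4% of failures, both arms | 90.4 vs 76.0 | 14.4 | 0.941 | 0.931 |
| 12% of failures, both arms | 91.2 vs 78.0 | 13.2 | 0.917 | 0.907 |
| 20% of failures, both arms | 92.0 vs 80.0 | 12.0 | 0.886 | 0.876 |
| active arm, 3 points (about 3) | 93 vs 75 | 18 | 0.997 | not run |

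On the one-stratum formula, power is below 90% at about 1.8 points in the withdrawal arm alone (0.018 × 213 ≈ 4 patients). With masking in both arms it is below 90% at about 17% of failures (0.17 × 0.25 × 213 ≈ 9 patients and 0.17 × 0.10 × 107 ≈ 2). For the stratified statistic these points are nearer 1.4 points (0.014 × 213 ≈ 3 patients) and 14%.

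**5. Part A**

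Design rates are 65% vs 5% (PASI 90) and 80% vs 5% (sPGA), with 400:100. Three points masked in placebo move the differences from 60 to 57 and from 75 to 72. With 20 points masked, 65 vs 25 gives SE = √(0.2275/400 + 0.1875/100) = 0.049 and 0.40/0.049 ≈ 8. Power stays above 99.9% for both endpoints.

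**The case against.** The SAP is silent rather than contrary. Section 3.0 says it elaborates the protocol's methods, so the rule could be read as still in force, and silence in 14.1 fits an intention to change nothing. This does not settle the matter. SAP 10.1.4 restates the retreatment rule and not this one, so a programmer has good reason to take its list as complete. Two defensible readings of responder status on a confirmatory endpoint are a defect in themselves.

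The group is small by design, and this stands. Intolerable worsening leads to leaving the trial, sPGA of 3 or more in Part B leads to retreatment, limited low-potency topical steroids are allowed, and a patient who stays must stop the prohibited drug. Relapsers retreated before Week 52 cannot be masked, so the larger scenarios draw on only part of the failures.

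The power figures also depend on the formula. Pooled variance at the minimum 102:204 gives 61% at 5 points in the withdrawal arm, against 71% above. They show sensitivity and are not forecasts.

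Protocol 7.5 attaches the rule to its binary imputation bullets and does not name MI. Extending it to MI is still reasonable, because the rule is worded for binary endpoints and the SAP treats retreatment the same way under NRI and MI.

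**Conclusion.** The concern holds and should be fixed. The prohibited-medication rule is missing from SAP 10.1.4 and 10.1.3, and 14.1 does not declare its absence. As written, the SAP gives some patients a different responder status from the protocol on the co-primaries and the Part B primary.

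That conclusion rests on the text alone and is firm. The size of the effect rests on assumed rates of use and on the design rates holding under the protocol rule. Part A significance is safe. Part B starts with about 95% power (94% stratified), so a handful of patients would mainly distort the effect estimate. About 3 or 4 masked failures confined to the withdrawal arm would be enough to take power below 90%.

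**What to change.** Before unblinding:

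- **SAP 10.1.4:** add that subjects who start prohibited medication to treat psoriasis count as non-responders at all later visits in the NRI and MI analyses. This also stops such visits from supporting the before-and-after exception.
- **SAP 10.1.3:** add first use of such medication as a failure event for time to loss of response, dated when first taken.
- **LOCF:** protocol 7.5 has no separate rule for this case, so the sponsor should choose and state the handling in that sensitivity analysis.
- **SAP 5.1:** consider restricted medication when the per-protocol criteria are finalised.
- **If the omission is intended:** declare and justify it in 14.1 instead.

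The cost is a few sentences and one derived flag. Protocol 4.2.1 already has concomitant and rescue therapies recorded on the eCRF. It does not say that the indication is captured, so deciding which uses were for psoriasis may need a blinded review. Response rates may come out slightly lower. Sample size and alpha do not change.

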5.0 Analysis Populations

5.1 Definition for Analysis Populations

Efficacy Population:

Intent-to-Treat (ITT) Population: The ITT Populations will be used for the efficacy analyses in different parts.

- The ITT Population in Part A1 (ITT_A1) is defined as all subjects who are randomized at Baseline. This Population will be analyzed for the efficacy of initial treatment.
- The ITT Population in Part A2 from Arm 1 (ITT_A2) is defined as all subjects who were randomized to Arm 1 at Baseline. Data from Part A2 will be used to evaluate the mid-term efficacy.
- The ITT Population across Part A2 and B from Arm 2 (ITT_ARM2) is defined as all subjects who were randomized to Arm 2 at Baseline and received at least one dose of study drug on or after Week 16. This Population will be analyzed for short and long term efficacy without initial loading dose.
- The ITT Population in Part B for re-randomized subjects (ITT_B_R) is defined as all subjects who were randomized to Arm 1 and re-randomized at Week 28. The ITT_B_R Population will mainly be used to compare efficacy of continued treatment with risankizumab vs withdrawal from the treatment. The risankizumab arm will also be summarized (including data after retreatment) for long-term efficacy with the option of re-load.
- The ITT Population in Part B for Arm 1 non-responders at Week 28 (ITT_B_NR) is defined as all subjects who were randomized to Arm 1 at Baseline, were non-responders (sPGA ≥ 2) at Week 28, and receive at least one dose of risankizumab on or after Week 28. This population will be summarized for potential delayed response.
- The ITT Population for Part B placebo patients who received retreatment (ITT_B_PBO_RT) is defined as all subjects who were re-randomized to placebo and received at least one dose of retreatment with open label risankizumab after relapse, and have the opportunity to have retreatment Week 16 assessments.

- The ITT Population for Part B risankizumab patients who receive retreatment (ITT_B_RZB_RT) is defined as all subjects who were re-randomized to risankizumab and received at least one dose of retreatment with open label risankizumab after relapse, and have the opportunity to have retreatment Week 16 assessment. The population will be summarized to examine the efficacy of re-treatment with loading dose upon relapse on risankizumab.

ITT Populations will be analyzed by the treatment group as randomized.

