In addition, additional analysis will be performed on ITT_B_R subjects who are re-randomized to risankizumab 150 mg, in which all evaluations after re-randomization (including evaluations after retreatment with open label risankizumab after relapse) will be included along with the blinded assessments to evaluate the efficacy of continuous treatment.

Per-Protocol (PP) Population: To evaluate the impact of protocol deviations on the primary and ranked secondary endpoints, additional analyses will be performed on the Per-protocol Populations. The Per-protocol Population will include those who were most compliant with the protocol in ways that could impact the primary and ranked secondary endpoints. Final results and the criteria for exclusion of subjects will be finalized prior to database lock for data pertaining to the DB period.

The PP Population at Part A1 (PP_A1; a.k.a. the PPS in study Protocol 1311.4) is defined as all subjects from the ITT_A1 Population who meet all the following criteria:

- Subjects must receive at least 75% of planned study drug injections, per randomization, in Part A1.
- Subjects must have either a PASI or sPGA assessment post-baseline in Part A1.
- Inclusion Criterion 4: Subjects must have stable moderate to severe chronic plaque psoriasis at baseline:
 - Have an BSA $\geq 10\%$ and
 - Have a PASI ≥ 12 and

- Have an sPGA ≥ 3 .

Primary and ranked secondary efficacy endpoints at Part A1 at Week 16 will be analyzed on the PP_A1 Population.

The PP Population at Part B for re-randomized subjects (PP_B_R; a.k.a. RRS-PPS in study Protocol 1311.4) is defined as all subjects from the ITT_B_R Population who meet all the following criteria:

- Subjects must receive at least 75% of planned study drug injections, per re-randomization, in Part B.
- Subjects must have at least one sPGA assessment post re-randomization in Part B.
- Subjects must have sPGA < 2 at re-randomization.

The primary efficacy endpoint for Part B at Week 52 and ranked secondary endpoint for Part B at Week 104 will be analyzed on the PP_B_R Population.

PP Populations will be analyzed by the treatment group as randomized (or re-randomized).

Safety Population:

The Safety Populations will be used for safety analyses in different study parts.

Each ITT population will have a corresponding safety population (Safety) of the same study part, which includes all subjects who receive at least one dose of study drug during the analysis period.

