Table 12. Visit Windows for Analysis of Other Efficacy Endpoints Collected at Week 28, 52, 76, and 104 in Part A2 and B (ITT_ARM2 Population)

Window Label	Target Day	Interval
Entry of A2	1	≤ 1
Week 28	85	[2, 169]
Week 52	253	[170, 337]
Week 76	421	[338, 519]
Week 104	617	[520, 715]

Rx Day calculated relative to first dose date of risankizumab.

Table 13. Visit Windows for Analysis of PASI and sPGA During Retreatment with Risankizumab (ITT_B_PBO_RT/ITT_B_RZB_RT Populations)

Window Label	Target Day	Interval
Entry of RTS	1	≤ 1
Week 8R	57	[2, 85]
Week 16R	113	≥ 86

Rx Day calculated relative to first dose date of retreatment with risankizumab.

Table 14. Visit Windows for Analysis of Other Efficacy Variables Only Collected at EOT and EOO Visits During Retreatment with Risankizumab (ITT_B_PBO_RT/ITT_B_RZB_RT Populations)

Window Label	Target Day	Interval
Entry of RTS	1	≤ 1
Week 16R	113	≥ 2

Rx Day calculated relative to first dose date of retreatment with risankizumab.

Table 15. Visit Windows for Analysis of Vital Signs and Local Tolerability in the ALL_RZB Population

Window Label	Target Day	Interval
Baseline	1	$\leq 1^a$
Week 4	29	[2, 43]
Week 8	57	[44, 71]
Week 12	85	[72, 99]
Week 16	113	[100, 155]
Week 28	197	[156, 239]
Week 40	281	[240, 323]
Week 52	365	[324, 407]
Week 64	449	[408, 491]
Week 76	533	[492, 575]
Week 88	617	[576, 673]
Week 104	729	[674, 785 ^b]

Rx Day calculated relative to first dose date of risankizumab.

- a. Local tolerability not measured at Baseline and at Week 104. If time is collected in vital signs, restrict to records prior to the first dose of risankizumab.
- b. The minimum of upper bound and within 105 days of last dose of risankizumab.

Table 16. Visit Windows for Analysis of Safety Laboratory Tests and ECG in the ALL_RZB Population

Window Label	Target Day	Interval
Baseline	1	≤ 1
Week 4	29	[2, 71]
Week 16	113	[72, 155]
Week 28	197	[156, 239]
Week 40	281	[240, 323]
Week 52	365	[324, 407]
Week 64	449	[408, 491]
Week 76	533	[492, 575]
Week 88	617	[576, 673]
Week 104	729	[674, 785 ^a]

Rx Day calculated relative to first dose date of risankizumab.

a. The minimum of upper bound and within 105 days of last dose of risankizumab.

The time windows specified in [Table 17](#), [Table 18](#), [Table 19](#), [Table 20](#), [Table 21](#) and [Table 22](#) will be used for the summary of study drug injections of each period.

Table 17. Visit Windows for Summary of Study Drug Injections for Part A1

Window Label	Target Day	Interval

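### SAP 10.1.4 drops the protocol's limit on counting retreated subjects as non-responders, so read literally the planned retreatment responder rate is 0% whatever is observed

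*SAP*

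**What the plan says.** SAP 10.1.4 ends its imputation rules with a note on retreated subjects. Those who "received retreatment with risankizumab for relapse during Part B, will be counted as non-responders in all visits thereafter in the NRI and MI analyses". The same sentence adds that they "will have their last observation prior to discontinuation or retreatment with risankizumab carried forward in the LOCF analyses". It names no population and gives no exception. Earlier in the section: "The NRI will be the primary approach in the analyses of categorical variables".

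Protocol 7.5 gives the rule a scope: "for randomized withdrawal analyses, subjects who received retreatment will be counted as non-responders in all visits after the date of retreatment".

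SAP 5.1 defines two populations for the response to retreatment. ITT_B_PBO_RT holds subjects re-randomized to placebo who "received at least one dose of retreatment with open label risankizumab after relapse, and have the opportunity to have retreatment Week 16 assessments". ITT_B_RZB_RT is its counterpart for subjects re-randomized to risankizumab: "The population will be summarized to examine the efficacy of re-treatment with loading dose upon relapse on risankizumab". Table 13 in SAP 6.0 gives both populations PASI and sPGA windows at Weeks 8R and 16R, counted from the first retreatment dose. SAP 10.1 has efficacy variables summarized in every efficacy population.

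SAP 5.1 also plans an additional analysis of the ITT_B_R subjects re-randomized to risankizumab, using all evaluations after re-randomization, "including evaluations after retreatment with open label risankizumab after relapse". The note to Table 8 repeats this.

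**The concern.** In the withdrawal comparison the rule is sensible. A subject who relapsed and was retreated has failed the assigned strategy, and a later recovery on open-label drug should not count for it. In a population made up entirely of retreated subjects, the same rule fixes the answer before any data are seen.

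Response to retreatment after relapse is an objective in the protocol synopsis, Protocol 2.2 and SAP 4.1, and Protocol 5.1.3 plans to analyse the further endpoints after retreatment. A 0% table would be noticed. The less visible risk lies where retreated subjects are only part of the denominator, as in the continuous-treatment analysis and ITT_ARM2. There the literal rule gives a plausible but lower rate, and two programmers could reasonably code it differently.

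**Working it through.** **1. The plan's own figure.** No retreatment response rate is stated, so the only related figure to reproduce is the size of the withdrawal comparison (Protocol 7.7): 90% versus 75% at Week 52, allocation 1:2, two-sided 0.05, 90% power.
- Pooled proportion: (0.90 + 2 × 0.75)/3 = 0.80.
- n(active) = [1.960 × √(0.80 × 0.20 × 1.5) + 1.282 × √(0.90 × 0.10 + 0.75 × 0.25/2)]² / 0.15² = (0.960 + 0.549)² / 0.0225 ≈ 101.3, rounded up to 102.
- This gives 102:204, with power 90.2%, and 306/0.8 = 382.5, rounded up to 383 at Visit 2. All agree with the protocol.

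The comparison keeps the non-responder rule under either scope, so limiting the rule leaves these figures unchanged.

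**2. The literal rule in the retreatment populations.** Inputs: every member was retreated after relapse (SAP 5.1); retreated subjects are non-responders at all later visits under NRI (SAP 10.1.4); Weeks 8R and 16R follow the first retreatment dose (Table 13). Responders = 0/N at both visits for any N, even if every subject is observed clear.

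The exact 95% upper limit for 0/N is 1 − 0.025^(1/N): 16.8% at N = 20, 7.0% at N = 51, 3.6% at N = 100. These N are arbitrary. They show that the table would look precise while carrying no information.

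**3. Whether another planned categorical method escapes.**
- MI covers only primary and ranked secondary endpoints, none of which is a retreatment endpoint.
- As-observed analysis is listed only for continuous variables.
- LOCF is ambiguous. The retreatment sentence carries forward the value before retreatment. For sPGA 0/1, a relapse score of 3 or more would again give 0%; for PASI endpoints the result need not be 0% but would not reflect retreatment. However, the LOCF definition in the same section allows carry-forward only within a period and excludes baseline values, and SAP 6.0 defines a final observation for a separate retreatment period. SAP 4.2, in contrast, describes Part B as including possible retreatment.

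**4. The continuous-treatment analysis.** Let N be the subjects re-randomized to risankizumab, s the responders at a visit who were never retreated, and t the retreated subjects observed as responders at that visit.
- Literal SAP 10.1.4: s/N.
- SAP 5.1 and the note to Table 8: (s + t)/N.
- Difference: t/N. The documents give no value for t.

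**5. ITT_ARM2.** Protocol 3.1 and 6.2.2 have any Week 28 responder who relapses retreated, which includes Arm 2. Arm 2 was never re-randomized, so the protocol's scope does not reach it, but the SAP's unlimited sentence does. Table 8 stops at the first retreatment dose, while Table 11, which governs ITT_ARM2, has no such cut. The SAP does not say which rule applies.

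**The case against.** The strongest reply is that the intent is plain. The SAP says that it elaborates the protocol, and the protocol supplies the limit. Separate retreatment populations with their own visit windows make sense only if post-retreatment observations are used. SAP 14.1 lists changes from the protocol and does not list this one, which is at least as consistent with no change being intended as with an undisclosed one. The NRI text also restricts the observations used to the same analysis period.

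This shows that 0% was not meant, and that part stands. It does not limit the sentence. The same-period wording governs which observations support an imputation; it does not narrow a rule covering all later visits.

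Three stronger readings are tempting, and the documents do not support them:
- *The rule cancels the continuous-treatment analysis and makes it identical to the withdrawal result.* SAP 5.1 provides for post-retreatment data twice and the note to Table 8 does so again. The text conflicts with itself; it does not settle the matter against that analysis.
- *LOCF certainly carries the relapse value into Weeks 8R and 16R.* The within-period and no-baseline wording leaves this open. Planned as-observed analyses of continuous variables would also still show the actual values.
- *At most 51 placebo-arm (0.25 × 204) and 10 active-arm (0.10 × 102) patients are affected, with an 80-point error.* The 25% and 10% are assumed losses of sPGA 0/1 at Week 52. Retreatment requires sPGA of 3 or more and can occur later, so these counts bound nothing. The 80% is the assumed response to initial treatment at Week 16, not a retreatment rate.

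**Conclusion.** The concern holds as a fault of scope in SAP 10.1.4. Taken as written, the primary categorical method gives 0/N responders at Weeks 8R and 16R in both retreatment populations. This rests only on the population definitions and the rule, with no assumption about response rates. The sentence also contradicts the planned inclusion of post-retreatment evaluations in the continuous-treatment analysis and leaves ITT_ARM2 undetermined. The effect of LOCF is ambiguous.

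A reader might infer that the confirmatory results are at risk. They are not. Retreatment cannot begin before Week 32, so Week 16 is untouched, and at Weeks 52 and 104 the rule does what Protocol 7.5 intends. The affected retreatment analyses carry no hypothesis test or alpha. The error cannot be sized beyond the literal 0%, because the documents state neither the number retreated nor a retreatment response rate. The wording should be corrected before database lock.

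**What to change.** In SAP 10.1.4:
- Limit the post-retreatment non-responder and carry-forward rules to the RZB/RZB/RZB versus RZB/RZB/PBO comparison in ITT_B_R and PP_B_R.
- State that ITT_B_PBO_RT, ITT_B_RZB_RT and the additional continuous-treatment analysis use observed post-retreatment assessments, with NRI or LOCF only for visits missing within the retreatment period.
- For ITT_ARM2, use observed post-retreatment values, consistent with Table 11, or state explicitly that the non-responder rule applies.

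The cost is a few sentences, with no new data and no change to the withdrawal sample size or power. It is best done before the lock for the Week 52 analysis, because Protocol 7.4 unblinds the sponsor for that analysis and a later choice between the readings would no longer be clearly pre-specified.
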